- 2 * Discuss the research design including but not limited to such issues as: probability of group assignment, potential for subject to be randomized to placebo group, use of control subjects, etc.:

Volunteers with a DSM-IV diagnosis of schizophrenia or schizoaffective disorder will be recruited, screened, and allocated in a double-blind manner to either the Nicotine Group or the Placebo Group. All participants will be asked to perform 10 weeks of cognitive remediation training (Posit Science, Duncan, SC), with daily training sessions Monday through Friday. On Mondays and Thursdays, all participants receive a lozenge 20 min prior to the training. In the Nicotine Group, the lozenge will contain 2 or 4 mg of nicotine, depending on smoking status. In the Placebo Group, the lozenge will be a matched placebo.

Outcome measures (OCMs) are assessed on Wednesdays in week 0 (day before training starts), weeks 4, 7 and 10 (after the training session), and week 14 (four weeks after training ends). OCMs are assessed on a non-drug day (Wed) because we are not studying the acute effects of nicotine but nicotine-induced enhancement of longer-term training effects.

- 3 * Describe the relevant prior experience and gaps in current knowledge. Describe any relevant preliminary data:

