
remind them to take the lozenge 20 min before the training. The participant would be allowed to keep up to two lozenges at home, for the event that they meet unexpected obstacles to coming to the MPRC on a lozenge day. Their performance would be monitored and recorded via an internet portal maintained by Posit Science Inc. Participants may take breaks but are encouraged to first complete the current exercise. We allow some flexibility in the above training and testing schedule because it will be unavoidable that some participants will be unavailable on some days. In general, if one lozenge session is missed, the lozenge will be given on the following day. If an outcome measurement day is missed, outcome measurements will be performed on either Tuesday or Friday of the same week (thus avoiding lozenge days), or if not feasible, in the preceding or following week. If an entire week of training is omitted by an otherwise reliable participant, the following weeks of the schedule will be moved back by one week.

- 2 * Describe all procedures already being performed for diagnostic or treatment purposes (if not applicable to the study, enter "N/A"):

N/A

- 3 * Describe the duration of an individual participant's participation in the study:

The cognitive training intervention will take 10 weeks. A follow-up outcome assessment session will be scheduled 4 weeks following training completion, but we will allow up to 10 weeks before a participant is labeled as "lost to follow-up". We will allow up to 3 months between consent and the next study session; after this, a participant would have to be re-consented. We will allow up to 3 months between the last nicotine exposure session and the beginning of the cognitive training. Thus, the maximum duration of participation is 12 months. If more than 3 months elapsed between the screening and the beginning of the training procedure, we would repeat most of the screening procedures prior to the start. A study physician would determine which procedure need to be repeated.

- 4 * Describe the duration of the entire study:

We anticipate that data collection will be completed in two years. Data analyses and preparation for publication may continue thereafter.

- 5 * Describe any additional participant requirements:

None.

ID: VIEW4E0280585B400

Name: v2_Study Procedures

View: v2_Sample Size and Data Analysis

Sample Size and Data Analysis

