
Hypothesis 2a (training progress within nicotine vs. placebo sessions): For those adaptive exercise parameters for which progress is stated at the end of each session, we will compare nicotine - placebo differences on within-session progress, averaged over 20 lozenge-sessions, between treatment groups using a t-test. Power is estimated from the formula⁷⁸ $d = [2(z_a + z_b)2(1-(b-1)r)/bn]$, where d = (difference in average change)/SD(change within 1 session), $b=20$ visits per subject, and other terms are defined as above. For $n=20$ completers per group, we would have power=0.80 at two-sided $\alpha=0.05$ to detect $d=0.51$ (a medium effect size) for $r=0.3$. r is estimated based on each exercise being short and of potentially low reliability. To test Hypothesis 2b (persistence of nicotine-induced improvements beyond the presence of nicotine), we will analyze within-session progress on no-lozenge sessions. If progress made in the nicotine sessions does not persist, we would expect a performance decrement in subsequent no-lozenge sessions (Tue, Fri), whose difficulty levels begin where the previous session left off. If progress made under nicotine does persist, we would expect no decrement and progress comparable to no-lozenge sessions in the placebo group.

To achieve 20 completers per group, we expect having to enroll 25 subjects per group into the training and having to screen approximately 70 subjects in total.

Please note that screening is part of the study protocol. Thus, we expect to consent 70 subjects.

- 2 * Provide the plan for data analysis. Include in the description the types of comparisons that are planned (e.g., comparison of means, comparison of proportions, regressions, analysis of variance, etc.), which is the primary comparison/analysis, and how the analyses proposed will relate to the primary purposes of the study:

Please see above. The sample size calculation is closely related to the planned analyses.

ID: VIEW4E02806052800

Name: v2_Sample Size and Data Analysis

View: v2_Sharing of Results

Sharing of Results

- 1 * Describe whether results (study results or individual subject results, such as results of investigational diagnostic tests, genetic tests, or incidental findings) will be shared with subjects or others (e.g., the subject's primary care physicians) and if so, describe how it will be shared:

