Participants will be asked to perform 10 weeks of computerized cognitive remediation training (Posit Science, Duncan, SC), with daily 80-min training sessions Monday through Friday, usually in the presence of a research assistant. Each cognitive remediation training session will include ~30 min of auditory and ~30 min of visual training exercises by Posit Science, in a counterbalanced manner. Both programs posit that the quality and quantity of processed sensory information form the basis for higher cognitive functions by affecting, e.g., processing speed and the availability of attentional resources. The auditory training consists of six exercises: fast and accurate discrimination of (1) sound frequencies, (2) phonemes and (3) syllables, and recall of syllables, (4) sequences of syllables, (5) multi-element verbal instructions, and (6) details of a narrative. The visual training consists of five exercises designed to (1) improve visual precision, (2) increase capacity to divide visual attention, (3) improve visual memory, (4) expand field of view, and (5) increase visual processing speed. Participants will perform ~15 min of an exercise at a time and complete five exercises per session. The aim is to complete each exercise twice/week and on at least one lozenge-day/week (Mon or Thur). Within these restrictions, we will aim at completing the sound frequency discrimination almost daily.

The programs train the fine-tuned and differentiated processing of sensory input and engage attention, working memory and/or executive processes. To induce the right level of challenge and promote engagement and motivation, task difficulty adjusts continuously to performance to maintain ~85% correct responses (rewarded by auditory and visual feedback). Adjustable parameters are presentation time, interstimulus interval, stimulus similarity, stimulus eccentricity, number of stimuli, and information complexity.

ID: VIEW4E0BC12A9F800
Name: v2_Behavioral Interventions

View: v2_Testing

Testing

You indicated that this study involves neuropsychological or psychophysiological testing.

If you uploaded a separate research protocol document in the 'Research Protocol' page, cite the applicable section and page numbers from that document in the answer boxes below.

- 1 * List all of the tests to be used in the study, including both standardized and non-standardized assessments:

The cognitive status of patients and controls will be assessed by the following tests:

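### Hypothesis 2b pools Tuesday and Friday runs without requiring that the same exercise was last run with a lozenge, which dilutes a true loss of gains and favours the finding that gains persist

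*Combined protocol and SAP*

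**What the plan says.** The test is described in Sample Size and Data Analysis, item 1. Within-session progress on no-lozenge sessions is analysed. If gains made under nicotine do not last, "we would expect a performance decrement in subsequent no-lozenge sessions (Tue, Fri), whose difficulty levels begin where the previous session left off". If they do last, "we would expect no decrement and progress comparable to no-lozenge sessions in the placebo group". The section gives Hypothesis 2b no named test, no margin for what counts as comparable, and no power figure.

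The timetable is set elsewhere:

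- Research Design (Justification, Objective, & Research Design, item 2) plans ten weeks "with daily training sessions Monday through Friday", and "On Mondays and Thursdays, all participants receive a lozenge 20 min prior to the training".
- Behavioral Intervention, item 1, lists six auditory and five visual exercises. Participants "complete five exercises per session. The aim is to complete each exercise twice/week and on at least one lozenge-day/week (Mon or Thur"). Sound-frequency discrimination is to be run almost daily.
- Study Procedures, item 1, says that only some exercises report progress after each session, without naming them, and that these values are recorded on all training days. Under the scheduling rules, "if one lozenge session is missed, the lozenge will be given on the following day".

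**The concern.** Hypothesis 2b treats a Tuesday or Friday run as the first off-drug run after a lozenge run, starting at the level reached under nicotine. Difficulty adapts within each exercise, so what matters is the last run of that exercise, not the last calendar session. If that last run was off-drug, any loss of a nicotine gain has already shown itself there, and the run being tested has no gain from an immediately preceding lozenge run to lose.

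Pooling such runs with the informative ones shrinks a real decrement. Absence of a decrement is the evidence for persistence, so the shrinkage favours confirming the hypothesis. Hypothesis 2b carries the plan's claim that nicotine acutely facilitates learning rather than only lifting performance while it is present. It is not the primary outcome, which is the MCCB.

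**Working it through.** The documents state no figure for Hypothesis 2b, so there is none to reproduce. The check counts how often a Tuesday/Friday run follows an off-drug run of the same exercise.

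**Inputs from the documents.** Five training days; lozenges on Monday and Thursday; five exercises per session; 6 + 5 = 11 exercises; each twice a week; sound frequency almost daily.

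**Assumptions.** Difficulty carries over per exercise, no exercise runs twice in one day, sound frequency runs all five days, no sessions are missed, and all runs get equal weight.

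**Slots.** 5 × 5 = 25 per week, which equals 5 for sound frequency + 10 × 2 for the rest. Lozenge-day slots: 2 × 5 = 10, fewer than 11 exercises. With sound frequency taking two, 8 remain for the other 10 exercises, so at least two exercises a week have no lozenge-day run. Tuesday and Friday hold 10 runs: 2 of sound frequency, always after a lozenge-day run, and 8 of the others.

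**Aim followed as far as slots allow, same timetable every week.** A twice-weekly exercise with one lozenge-day run always has that run before its Tuesday or Friday run (Mon-Tue, Mon-Fri, Tue-Thu, Thu-Fri: 4 of 4). The two uncovered exercises use Tue-Wed, Tue-Fri or Wed-Fri, which supply 1, 2 or 1 Tuesday/Friday runs, all after an off-drug run. With the three pairs equally likely:

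- expected off-drug-preceded runs = 2 × (1 + 2 + 1)/3 = 2.67 per week
- share of the ten other exercises = 2.67/8 = 33%
- share of all Tuesday/Friday runs = 2.67/10 = 27%

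**Aim followed, timetable reshuffled weekly.** Each of the six covered patterns has probability 0.8/6 = 0.133, and each of the three uncovered ones 0.2/3 = 0.067.

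- The last run of a week is on a lozenge day only for Tue-Thu and Wed-Thu: 2 × 0.133 = 0.267.
- Lozenge-preceded Tuesday/Friday runs per exercise-week: 3 × 0.133 (Mon-Tue, Mon-Fri, Thu-Fri) + 0.133 × 0.267 (Tue-Thu) + 2 × 0.067 × 0.267 (the Tuesday runs of Tue-Wed and Tue-Fri) = 0.471.
- All Tuesday/Friday runs per exercise-week: 8/10 = 0.8.
- Off-drug-preceded share: (0.8 − 0.471)/0.8 = 41%. Over all runs: 10 × 0.329/10 = 33%.

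Simulated ten-week schedules reproduce these values. Counting week 1, where an exercise's first run has no predecessor and drops out, lowers them by up to about one point. This gives 26% (fixed) to 32% (reshuffled) of all Tuesday/Friday runs, and 33% to 40% without sound frequency.

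**Aim ignored.** The ten possible day pairs contain 8 Tuesday/Friday runs. On a fixed timetable 4 follow a lozenge day and 4 do not, so the share is 4/8 = 50%, or 4/10 = 40% with sound frequency included. Reshuffling changes this by about one point.

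**Dilution.** If a true loss δ shows only in lozenge-preceded runs and a share s of runs are not of that kind, the pooled decrement is (1 − s)δ. With the aim followed, s = 0.26 gives 0.74δ and s = 0.40 gives 0.60δ. With the aim ignored it is 0.60δ, or 0.50δ without sound frequency.

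**The case against.** Several points on the other side stand.

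- **A next-day repeat is not needed.** A reader might infer that because most exercises run on Monday are not run again on Tuesday, there is nothing to lose. The plan says difficulty starts where the previous session left off, not where yesterday ended. A Friday run after a Monday lozenge run still starts at Monday's level. Of the four covered Tuesday/Friday runs above, only two fall on the day after the lozenge, yet all four are informative.
- **Much larger shares are not supported.** A reader might arrive at 40-76% of the tested runs. The upper end needs strict rotation through the ten other exercises (Mon 1-4, Tue 5-8, Wed 9, 10, 1, 2, Thu 3-6, Fri 7-10). That never gives exercises 7-10 a lozenge day, against the plan's own aim, and it leaves sound frequency out of the count.
- **Make-up lozenges.** A Tuesday with a make-up lozenge is a lozenge session, so the phrase 'no-lozenge sessions' arguably excludes it already. The documents do not show that on-drug days enter the test.
- **Wednesdays.** That same phrase arguably includes Wednesday, and (Tue, Fri) may only say where a decrement is expected. This does not remove the problem. On the fixed timetable with the aim followed, pooling all three days gives (2.67 + 1.33 + 1)/15 = 33% off-drug-preceded runs. The 1.33 are Wednesday runs of the two uncovered exercises (2 × 2/3), and the 1 is Wednesday's sound-frequency run, which follows Tuesday's.
- **Unknown mix of exercises.** The exercises with per-session progress are not named. If they are mainly sound frequency run daily, the Tuesday/Friday share is near zero.

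**Conclusion.** The point holds as a gap in how the tested runs are selected. The plan does not tie a tested run to a preceding lozenge run of the same exercise, and its own timetable means that some tested runs follow an off-drug run. With the lozenge-day aim followed as far as slots allow, this affects about 26-32% of all Tuesday/Friday runs, or 33-40% without sound frequency. A true loss then appears at roughly 0.6-0.75 of its size, which favours a conclusion of persistence. If the aim is ignored, the shares are about 40% and 50%.

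These figures rest on the assumptions listed with the calculation and on all exercises contributing data; the real share may be anywhere down to near zero. The count of five per session is also not secure: about 30 + 30 minutes of exercises does not match five exercises of about 15 minutes (75 minutes) in an 80-minute session, and those passages need reconciling. The documents do not support a claim that most tested runs are uninformative. This is a cheap improvement to a mechanistic hypothesis and does not affect the primary analysis.

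**What to change.** In the Hypothesis 2b paragraph, replace (Tue, Fri) with a rule applied per exercise. The test set is every run made without a lozenge (Tuesday, Wednesday or Friday, by actual administration date) whose immediately preceding run of the same exercise was made with a lozenge. Apply the rule identically in both groups, counting placebo lozenges as lozenges. Compare groups on the change from the end level of that lozenge run. Use no-lozenge runs preceded by an off-drug run as a negative control, where no such decrement is expected. Name the exercises that report progress after each session.

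The cost is analysis wording only, because these values are already recorded on all training days. Fewer Tuesday/Friday runs enter, partly or wholly offset by Wednesdays. Under the assumptions above, with the aim followed:

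- fixed timetable: (10 − 2.67) + (4 − 1.33) = 10.0 eligible runs a week, against 10 Tuesday/Friday runs now
- reshuffled timetable: (10 − 3.29) + 4 × 0.467 = 8.6, where 0.467 is the simulated share of Wednesday runs of the ten other exercises that follow a lozenge-day run

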- 1 * Provide a summary of the background and purpose of the study in language that can be understood by a person without a medical degree.

Schizophrenia is marked by problems in attention, memory and problem solving. These deficits predict long-term functional outcome such as the ability to live independently and maintain employment, but they are not ameliorated by currently available medications. Cognitive training improves these functions to some degree, but this approach is very time- and resource-intensive. The current project aims at enhancing and accelerating the benefits that people with schizophrenia derive from cognitive training by administering nicotine during some of the training sessions. This would provide the proof of principle for a treatment intervention that can improve cognitive symptoms of schizophrenia.

ID: VIEW4E02805CF7000
Name: v2_Lay Summary

View: v2_Justification, Objective, & Research Design

Justification, Objective, & Research Design

If you uploaded a separate research protocol document in the 'Research Protocol' page, cite the applicable section and page numbers from that document in the answer boxes below.

- 1 * Describe the purpose, specific aims, or objectives of this research. State the hypothesis to be tested:

The current project aims at determining whether the intermittent presence of nicotine during cognitive training exercises in people with schizophrenia will shorten the training period necessary to induce significant and clinically relevant improvement and enhance the improvement seen after a training period of specified length. Hypothesis 1a: Nicotine administration during training will increase the size of all measured effects of the training intervention, and will accelerate the time course of performance enhancement on the MCCB and training exercise progression parameters.

Hypothesis 1b: The larger training effects in the Nicotine Group will persist beyond the end of the intervention.

Hypothesis 2a: Within-session progress on the training exercises will be larger in the presence of nicotine than in the presence of placebo.

Hypothesis 2b: These acute nicotine-induced performance elevations will persist beyond the presence of nicotine through subsequent non-drug training sessions, giving evidence of an acute facilitation of learning processes.

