If you uploaded a separate research protocol document in the 'Research Protocol' page, cite the applicable section and page numbers from that document in the answer boxes below.

- 1 * Provide the rationale and sample size calculations for the proposed target population:

Statistical and power analyses: Hypothesis 1a (larger or faster improvement in Nicotine than Placebo Group): Assuming training effects are linear with time, we will conduct an intention to treat (ITT) analysis by fitting the mixed model regression for repeated measures OCM= time+ treatment+ treatment x time, with time as a continuous measure. The treatment x time interaction estimates the difference between treatment groups in OCM rate of change (slope). Although we will include subjects with partial data, the effect size detectable was estimated conservatively⁷⁸ by: $d = [2(z_a + z_b)2(1-r)/bnVar(t)]/2$, where d = (difference in slopes)/SD(OCM), r = within-subject correlation of OCM, $b=4$ visits per subject, n = number of completers per group, $Var(t)=0.185$ is the within-subject variance of the visit times, and $z_a=1.96$ and $z_b=0.84$ for two-sided $\alpha=0.05$ and power=0.80. With $n=20$ completers per group, $d=0.56$ (a medium effect size) will be detectable for $r=0.7$ consistent with the high ICC of the MCCB, the primary OCM. To explore differences in treatment effects between MCCB domains, we will employ the mixed model for repeated measures: T-score= domain+ treatment+ time+ interactions. In particular, the domain x treatment x time interaction assesses variation among domains in the magnitude of the treatment effects on change slopes in OCM scores. In secondary analyses to guide the design of future studies, we will fit a model in which time is treated as a categorical measure unconstrained by a linear fit to explore different learning scenarios such as a more rapid initial acquisition but similar ceiling. In this model, we will add week 14 data to examine Hypothesis 1b (persistence of improvements after training ends), comparing treatment groups on the difference between week 14 and 10. Other exploratory analyses: 1) Smoking status (smoker, never-smoker) is added as an exploratory between-subject factor. 2) A further regression will explore differences between treatment groups in two compliance measures, the cumulative percentage of missed training sessions and lozenge administrations until each OCM time point. If treatment groups differ on compliance, we would include time-dependent compliance as a mediator of treatment effects. A descriptive analysis to support Hypothesis 1a will compare the percentage of participants in each group that achieves clinically significant improvement in MCCB composite scores (6 points from baseline adjusted for practice effects, see above) at each OCM time point.

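### Hypothesis 2b would be supported by an absence of difference, with no margin or confidence-interval rule and no requirement that Hypothesis 2a first show a gain

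*Combined protocol and SAP*

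**What the plan says.** Justification, Objective, & Research Design, item 1, states Hypothesis 2b: "These acute nicotine-induced performance elevations will persist beyond the presence of nicotine through subsequent non-drug training sessions". The plan treats this as evidence that nicotine facilitates learning.

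The analysis is in Sample Size and Data Analysis, item 1: "we will analyze within-session progress on no-lozenge sessions". Two expected patterns follow. If progress is lost, "we would expect a performance decrement in subsequent no-lozenge sessions (Tue, Fri), whose difficulty levels begin where the previous session left off". If it is kept, "If progress made under nicotine does persist, we would expect no decrement and progress comparable to no-lozenge sessions in the placebo group".

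No test, margin, interval rule, power or adjustment for starting level is given for 2b. Item 2 of the same section, which asks for the analysis plan, only refers back to this text. The one power figure for within-session progress belongs to Hypothesis 2a: a detectable difference of d = 0.51 with 20 completers per group.

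**The concern.** The pattern that supports 2b is a null pattern. The noisier the data, the more likely the groups are to look comparable, so imprecision favours the hypothesis. The same pattern appears if nicotine produced no gain at all, because there is then nothing to lose, and the plan does not make 2b conditional on 2a.

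There is a second, smaller difficulty. The no-lozenge sessions are ones "whose difficulty levels begin where the previous session left off". If the gains are fully kept, the Nicotine Group starts them at a harder level than the Placebo Group. If learning slows as level rises, its progress is smaller although nothing was lost.

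At stake is a claim of lasting facilitation of learning that the data may not support.

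**Working it through.** **Inputs from the documents.** Sample Size and Data Analysis, item 1: n = 20 completers per group, b = 20 sessions, r = 0.3, z values 1.96 and 0.84, d = 0.51. Behavioral Intervention, item 1: each exercise is to be run about twice a week, at least once on a lozenge day. That leaves about one no-lozenge run per week for most exercises, or about 10 over 10 weeks.

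**Assumptions.** The 2a variance structure carries over to 2b, since the plan gives no inputs for 2b. SD means the SD of change within one session.

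**Reproducing the plan's figure.** d = √[2(z_a + z_b)²(1 + (b − 1)r)/(bn)] = √[2 × 7.84 × 6.7/400] = 0.512, which agrees with 0.51. This needs a plus sign before (b − 1)r and a square root. The formula as it reads in the text has a minus sign and no root, which may come from the PDF conversion.

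**Precision for 2b.**
- b = 20: variance of a participant's mean = 6.7/20 = 0.335. SE of the group difference = √(2 × 0.335/20) = 0.183. The 95% CI half-width is 1.96 × 0.183 = 0.36, about 70% of a 0.51 gain.
- b = 10: variance = 3.7/10 = 0.37. SE = √(2 × 0.37/20) = 0.192.

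**Chance that a real loss goes undetected**, 1 − Φ(loss/SE − 1.96):

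| Gain (SD) | Share lost | Missed, b = 20 | Missed, b = 10 |
|---|---|---|---|
| 0.51 | all | 20% | 25% |
| 0.51 | half | 71% | 74% |
| 0.51 | quarter | 90% | 90% |
| 0.30 | all | 63% | 66% |
| 0.30 | half | 87% | 88% |

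For example, half of 0.51 is 0.255; 0.255/0.183 = 1.393; Φ(1.393 − 1.96) = 0.285, so about 71% are missed.

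**What it takes to show persistence.** With one-sided 0.025, 80% power and no true loss, n per group is about 2 × 7.85 × 0.335/margin². Excluding total loss (0.51) needs 21 per group, half loss (0.255) 81, and quarter loss (0.1275) 324. With the planned 20 completers, the chance of excluding a half loss when nothing is lost is 29% (b = 20) or 26% (b = 10).

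**Flattening curve (shape assumed).** Let progress per run be k × (ceiling − level), with nicotine multiplying k by 1.25 to 2 on lozenge days and zero loss. With an exercise run every weekday, and placebo reaching 30%, 50%, 80% or 95% of ceiling by week 10, no-lozenge progress in the Nicotine Group falls below placebo by about 8%, 15%, 34% or 54% of the lozenge-day gain. With one lozenge and one no-lozenge run per week, k of 1% to 10% and a 1.5-fold boost, the shortfall is 6% to 59%. It is near zero if learning is near-linear. Progress stays positive. At a 0.51 gain, even 59% is 0.30 SD; 0.30/0.192 = 1.56, so it would reach significance in about 34% of trials.

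**The case against.** The plan describes expected patterns. A reader might infer that it declares a non-significant test to be proof of persistence, but it says no such thing. That is fair, yet no other basis for a conclusion is given, so an analyst following the text would have only the absence of a difference to report.

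A reader might also infer that the analysis cannot tell persistence from loss at all. It can in part: total loss of a gain as large as 0.51 SD would be detected in about 80% of trials. The weakness lies in partial loss and in smaller gains.

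A third tempting reading is that persistent gains on a flattening curve would be read as loss. The plan's sign of loss is a decrement, and flattening gives smaller but positive progress, which fits neither stated pattern. The documents do not give the curve. They foresee a ceiling only in the secondary analysis of the outcome measures. What stands is that the shortfall can be mistaken for partial loss. Taking decrement in the absolute sense does not rescue the rule, because a partial loss smaller than a session's ordinary progress would also leave progress positive.

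Finally, 2b is not the only evidence on learning as opposed to momentary performance. Outcome measures are taken on non-drug days, and Hypothesis 1b looks at week 14. That limits the severity.

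**Conclusion.** The concern holds at moderate severity. Hypothesis 2b would be supported by an absence of difference, without a bound on the loss to be excluded and without a prior gain under 2a. If the 2a inputs carry over, half loss of a 0.51-SD gain passes unnoticed in about 71% to 74% of trials and total loss in about 20% to 25%; with a 0.30-SD gain, total loss passes in about 63% to 66%. This part needs no assumption about the learning curve. The flattening effect is secondary: its direction is clear, but its size rests on an assumed curve. The primary MCCB analysis is not affected.

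**What to change.** Rewrite the 2b analysis as follows.

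1. Interpret 2b only if 2a shows a gain.
2. Classify runs per exercise by whether that exercise's previous run was actually a lozenge run. Study Procedures allows a missed lozenge to move to the next day, so the calendar day is not enough.
3. Report the group difference with a 95% CI, adjusted for the starting level of that exercise. Alternatively, compare the level recorded in the next no-lozenge run of an exercise with the level reached in its lozenge run. Starting level is itself affected by treatment, so show the unadjusted result as well.
4. Claim persistence only if the CI excludes a loss larger than a pre-stated share of the 2a gain, for example half. If the share refers to the estimated gain, the interval must carry the uncertainty of that estimate. Otherwise report 2b as inconclusive.

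Wednesday should not serve as a lozenge-free reference. With most exercises run about twice a week, a Wednesday run usually follows that exercise's own lozenge run. In the curve model with one lozenge and one no-lozenge run per week (1.5-fold boost), total loss gives a Tuesday/Friday-minus-Wednesday contrast of only +0.01 to +0.09 of the acute gain, so the loss would not show.

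The cost is analysis wording. For the exercises that report progress after each session, the values are already to be recorded on all training days. The downside is that inconclusive becomes a likely outcome: with the raw contrast, the chance of excluding a half loss when nothing is lost is only about 26% to 29%.
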